11.1 Analysis sets

For all analysis sets, subjects will be analyzed according to the study treatment(s) received.

The full analysis set will include all subjects that received any study drug and had any post-baseline assessment.

The safety analysis set will include all subjects that received any study drug.

The PK analysis set will include all subjects with at least one available valid (i.e. not flagged for exclusion) PK concentration measurement, who received any study drug and with no protocol deviations that impact on PK data.

11.2 Subject demographics and other baseline characteristics

All data for background and demographic variables will be listed by treatment sequence and subject. Summary statistics will be provided for all subjects, as well as for each treatment sequence.

Relevant medical history, current medical conditions, results of laboratory screens, drug tests and any other relevant information will be listed by treatment sequence and subject.

All available data under safety analysis set will be used for reporting purpose.

11.3 Treatments

Data for study drug administration and concomitant therapies will be listed by treatment sequence and subject.

All available data under safety analysis set will be used for reporting purpose.

11.4 Analysis of the primary variable(s)

The mean of multiple sleep latency scores is the primary variable of this study.

11.4.1 Primary Variable(s)

Each subject will undergo a sleep latency test assessment at each period, at approximately 1:30, 3:30, 5:30 and 7:30 in Day 2 (Night 1) and Day 3 (Night 2) (Days 12 and 13 in Treatment Period 2). The mean value of all the sleep latencies from a subject within a period will be defined as mean sleep latency score for that subject for that period.

11.4.2 Statistical model, hypothesis, and method of analysis

Nicotine is a powerful substance to stimulate wakefulness and attention. At same time screening MSLT reflects the stage of severity of shift work disorder patients. Therefore both smoking status (/nicotine intake) and MSLT at screening will be considered as covariates in the model.

For statistical analysis purposes; subjects under full analysis set with all available MSLT information from both the periods will be included in the analysis.

Mean sleep latency score data will be analyzed using a mixed effect ANOVA model with treatment smoking status at screening, screening MSLT, treatment interaction with screening MSLT and smoking status and period as fixed effects and subject as a random effect. Least square estimates for each treatment and treatment difference (LML134 vs placebo) along with 95% confidence interval will be reported. In studies with short treatment duration in SWD patients or healthy shift workers the usual approach is to compare post-dose conditions and not change from baseline. The reason for this approach is the high variability in MSLT (average of at least three tests is needed as baseline) and that baseline and post-dose MSLT results need to be time matched, as MSLT results depend on circadian rhythm.

The following assessments will be performed to judge efficacy of LML134:

a. Statistical significance: One sided (superiority) p-value of LML134 vs placebo from above fitted ANOVA model will be reported.

A p-value <0.1 will be considered as a positive sign for statistical significance.

b. Estimate of treatment difference (LML134 vs Placebo) will be reported.

An estimate of treatment difference > 1 minute would be considered as significant.

In addition from the above model, effect of LML over placebo in each subgroup (smoking status and MSLT (<6 and ≥ 6)) will be estimated through 95% CI of interaction effects.

Same analysis will be performed at interim.

Graphical display:

Subjects under safety analysis set will be used for reporting. For a thorough investigation of sleep latency time profiles, data from LML134 and placebo will be superimposed using suitable graphical tools like boxplot or arithmetic mean (SD) statistics.

Descriptive summary:

Subjects under safety analysis set will be used for reporting. Sleep latency data will be summarized by treatment and time point. Summary statistics like N, mean, SD, CV, and range will be reported.

11.4.3 Handling of missing values/censoring/discontinuations

If a subject has missing data at any timepoint during night 1 the corresponding timepoint from night 2 will be used to impute the value and vice versa. If a subject has a timepoint missing for both night 1 and 2 then MSLT will be calculated over all the available time points.

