3.2 Rationale of study design

Overall study design:

A cross-over study is planned to minimize the number of subjects and control for intra-subject variability during treatment comparison. The use of a subject and investigator-blinded placebo arm is to provide a comparison group for an unbiased collection of efficacy, safety, and tolerability data.

The purpose of the relatively long screening period is to allow time to establish the diagnosis of SWD according to ICSD-3 criteria, which requires assessment of the subject's circadian rhythm over a period of at least two weeks to demonstrate a disturbed sleep and wake pattern determined by a clinical interview and sleep diary data.

During the baseline period, each subject's circadian rhythm needs to be evaluated again with sleep diary data (which provides parameters such as total sleep time, time of going to bed and time of getting out of bed). This is necessary to inform about the subject's sleep-wake cycles for both treatment periods, as MSLT results can be substantially influenced by duration and quality of sleep before the assessment.

Subjects are required to stay at the sleep center for the entire treatment period, as the primary readout (MSLT) can only be performed at specialized centers.

Choice and timing of efficacy assessments:

The MSLT, which is considered the gold-standard objective measure of sleepiness, was selected as the primary readout to demonstrate the wakefulness promoting effect of LML134. It has successfully been used in previous studies in SWD patients to demonstrate drug effect on sleepiness.

Corporate Confidential Information

Congruous to the timing of excessive sleepiness in SWD patients, all efficacy assessments will be performed during the night.

Wakefulness will be assessed at regular intervals during the treatment nights, as recommended by relevant guidelines (Littner et al 2005) and also performed in other studies in SWD patients (Czeisler et al 2005; Czeisler et al 2009). MSLT will be timed such that they cover most of the regular interval corresponding to night shifts and the commute home (22:00 to 8:00), as this is the period when SWD patients could benefit from the effect of a wakefulness promoting drug. However, and MSLT will not be performed during the earliest hours of the shift, as no substantial impairment is expected then.

Safety assessments:

Corporate Confidential Information

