6.1.3.1 Handling of missing values/censoring/discontinuations

If a subject has missing data at any time-point at night 1(2), then the missing observation will be imputed as average of observed values from nearest neighbourhood of that day.

Corporate Confidential Information

If all observations at a night are missing the values from other night will be used for MSLT evaluation.

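### The missing-nap rules do not keep a subject's LML134 and placebo scores on the same clock times; the effect is small, of unknown direction, and cheap to remove

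*Protocol*

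**What the plan says.** Protocol 11.4.1 places naps at about 1:30, 3:30, 5:30 and 7:30 on each of two nights and sets the score: "The mean value of all the sleep latencies from a subject within a period will be defined as mean sleep latency score".

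Protocol 11.4.3 fills a nap missing on one night with the same clock time from the other night. For a clock time lost on both nights it adds: "If a subject has a timepoint missing for both night 1 and 2 then MSLT will be calculated over all the available time points".

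SAP 6.1.3.1 has a different rule. A missing nap takes the average of the closest observed naps on the same night. For a whole night: "If all observations at a night are missing the values from other night will be used for MSLT evaluation". Part of that section is redacted, so only the visible text can be judged.

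Protocol 11.4.2, explaining why change from baseline is not used, says that baseline and "post-dose MSLT results need to be time matched, as MSLT results depend on circadian rhythm".

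On who is analysed, protocol 11.4.2 takes full-analysis-set subjects with MSLT from both periods. SAP 6.1.3 uses the full analysis set with a subject random intercept.

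**The concern.** In a crossover the treatment effect rests on the difference between two scores from the same subject. If one score covers all four clock times and the other covers fewer, or has late naps filled from early ones, that difference contains a time-of-night component. Clock time is also time since dose: the naps fall 3.5, 5.5, 7.5 and 9.5 hours after dosing.

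The first part of protocol 11.4.3 preserves clock-time matching within a period. The visible SAP rule gives that up. A 7:30 nap lost on one night only is filled from earlier naps of that night, although the other night's 7:30 value exists.

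What is at stake is the estimate and its one-sided p-value. No visible planned analysis would show the problem. The log-scale analysis uses the same score, and SAP 6.2.3.1 sends the by-time model to the same imputation rule.

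**Working it through.** **The plan's own figure.** Inputs from protocol 11.7: true effect 2 min, SD 4 min, 36 evaluable subjects, p < 0.1 (one-sided, per 11.4.2), estimate > 1 min. Taking SE = 4 × √(2/36) = 0.943, the significance cut-off is 1.2816 × 0.943 = 1.208 min. P(estimate > 1.208 | 2) = 79.9%, against 80.0% in Table 11-1. P(estimate < 1 | 2) = 14.4%, as in the table. At 18 subjects the same formula gives SE = 4 × √(2/18) = 1.333 and a cut-off of 1.709 min. Both cut-offs exceed 1 min, so the p-value criterion is the binding one.

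**Shift in one period's score.** The documents give no latency by clock time. Assume a linear fall of d minutes from 1:30 to 7:30, with d = 2 to 6. Latencies relative to 1:30 are 0, −d/3, −2d/3 and −d, and the full mean is −d/2. The SAP's neighbourhood is read as the nearest observed nap or naps.

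- 7:30 lost on both nights, protocol: mean of the first three is −d/3, a shift of d/6 = 0.33 to 1.0 min.
- 7:30 lost on both nights, SAP: 7:30 takes the 5:30 value, the mean is −5d/12, a shift of d/12 = 0.17 to 0.5 min.
- 7:30 lost on one night only: protocol shift 0. SAP shift is half of d/12, that is d/24 = 0.08 to 0.25 min.
- Stop after the 1:30 nap of Night 1: the score is the 1:30 value under both rules, a shift of d/2 = 1 to 3 min.
- Stop after completing Night 1: all four clock times are present, so the shift is 0 under both rules.

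**Shift in the treatment difference.** Give each subject with two scores a weight of 1/n (balanced sequences, covariates ignored). For the stop after 1:30, (d/2)/18 = 0.056 to 0.167 min. If that subject is additional to the 18 completers, (d/2)/19 = 0.053 to 0.158. Three such subjects on one treatment at n = 18 give 0.17 to 0.50. At n = 36, one gives 0.028 to 0.083.

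**Effect on the false-positive chance.** Suppose four subjects, all on LML134, each have a score shifted by +1 min. At n = 18 the difference moves by 4/18 = 0.22 min and the chance goes from 10.0% to 13.2%. At n = 36 it moves by 0.11 min and the chance goes to 12.2%.

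**Direction.** The score shift in minutes (protocol rule / SAP rule) for other assumed profiles:

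| Profile over the four naps | Stop after 1:30 | Stop after 3:30 | Stop after 5:30 | 1:30 lost both nights |
|---|---|---|---|---|
| Fall of 1 min per nap | +1.5 / +1.5 | +1.0 / +0.75 | +0.5 / +0.25 | −0.5 / −0.25 |
| Rise of 1 min per nap | −1.5 / −1.5 | −1.0 / −0.75 | −0.5 / −0.25 | +0.5 / +0.25 |
| Trough at 5:30 (1, 0, −2, 1) | +1.0 / +1.0 | +0.5 / +0.25 | −0.33 / −0.75 | −0.33 / −0.25 |
| Recovery at 7:30 only (−0.5, −0.5, −0.5, 1.5) | −0.5 / −0.5 | −0.5 / −0.5 | −0.5 / −0.5 | +0.17 / 0 |
| Flat | 0 | 0 | 0 | 0 |

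The sign depends on the profile and on which nap is lost. The SAP rule usually shrinks the shift but can enlarge it when there is a trough.

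**The case against.** The strongest case on the other side has four parts.

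*The time-matching sentence is about something else.* It concerns baseline versus post-dose. A reader might infer that the protocol itself demands time matching between treatments; it does not say so. Its stated reason, dependence on circadian rhythm, does carry over to two post-dose means, but that step is an inference.

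*No direction is documented.* A reader might infer that the error favours the treatment on which a subject stops, and so LML134. That needs latency to shorten from 1:30 to 7:30 and more early stops on active drug. The nearest support is protocol 3.2: "MSLT will not be performed during the earliest hours of the shift, as no substantial impairment is expected then". That describes hours before the first nap, not the course between naps, and nothing in the documents shows more early stops on LML134. The inference does not stand.

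*Few subjects can be affected.* A within-subject mismatch needs a score in both periods. A missed dose ends treatment (protocol 7.2), so for early stops the mismatch arises mainly in Period 2. A Period 1 stopper is left out by protocol 11.4.2. Under the SAP's full analysis set that partial score may enter, but through between-subject information and not at weight 1/n. Naps lost without stopping remain possible in either period.

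*The size is assumed and small.* This stands. Entry requires a mean screening latency of at most 8 minutes, so d = 6 is a large change.

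A by-time mixed model is already planned (protocol 11.5.1, SAP 6.2.3), which is close to the remedy, but the SAP applies it after the same imputation.

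**Conclusion.** The gap is real and minor. Neither protocol 11.4.3 nor the visible text of SAP 6.1.3.1 requires a subject's two scores to cover the same clock times, and the SAP rule drops matching that the protocol kept for a nap lost on one night. The direction cannot be determined from the documents.

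The largest single-subject effect examined, a stop after the first 1:30 nap, is about 0.06 to 0.17 min on the treatment difference at n = 18, against an SE of about 1.33 min. This rests on a linear change of 2 to 6 min across the night, equal weighting of subjects with two scores, and the plan's SD of 4 min used as in Table 11-1. The effect is zero if no subject is affected or the profile is flat. It is a reason to tighten the rule, not a reason to doubt the design.

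**What to change.** In SAP 6.1.3.1, and in protocol 11.4.3 so that the two agree:

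1. Fill a missing nap first from the same clock time on the other night of that period.
2. If a clock time has no observed value in one period, either (a) score both of the subject's periods on the clock times observed in both, or (b) estimate the primary contrast from observed nap-level data without imputation, with clock time and treatment-by-clock-time as fixed effects and the four clock times weighted equally.

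Option (b) also handles a subject with only one period.

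The cost is a sentence or two of text and minor programming, on data already collected. Under (a) a few observed naps go unused, and if the drug effect varies over the night, the affected subject's contrast describes only the shared clock times. Option (b) avoids this but relies on the model for the missing naps.

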11.4.4 Sensitivity analyses

Mean of multiple sleep latency score is essentially a positive outcome. Thus a supportive analysis will be performed using log transformed mean sleep latency scores. Log transformed mean sleep latency score data will be analyzed using a mixed effect ANOVA model with treatment and period as fixed effects and subject as a random effect. Least square estimates for each treatment and treatment difference (LML134 vs placebo) along with 95% confidence interval will be back transformed to report in original scale.

11.4.5 Supportive analysis

The analysis explained in [Section 11.4.2](#) will be performed in a Bayesian platform with non-informative priors for treatment effects. The probability of treatment difference more than 0 and 1 will be reported to assess the similarity with primary analysis.

Futility Analysis:

The same analysis will be performed during interim analysis. The predictive distribution of treatment effect given the available data at interim will be evaluated to assess the chance of meeting proof of concept criteria at the end of complete trial. Explicit decision criteria for interim will be discussed in statistical analysis plan.

11.5 Analysis of secondary variable(s)

Overall safety profile is assessed by AEs, laboratory data, and ECG. Additionally, pharmacokinetics and MSLT scores are assessed under safety.

11.5.1 Efficacy / Pharmacodynamics

Subjects with all available MSLT assessments from both the periods under full analysis set will be used for reporting.

Here we want to take a look at sleep latency more vividly; i.e. rather than looking at overall score we need to look at the score of each time point separately.

Each subject will undergo a sleep latency test assessment at each period, at approximately 1:30, 3:30, 5:30, and 7:30 in Day 2 (Night 1) and Day 3 (Night 2) (Days 12 and 13 in Treatment Period 2). The mean value of sleep latencies averaged over two consecutive nights for each time point for each subject in each period will be defined as sleep latency score for that time point for that subject.

An arithmetic mean +/- SD time profile (time-points: 1:30 AM, 3:30 AM, 5:30 AM, and 7:30 AM) plot will be provided for each treatment. A summary table will be created to report n (number of evaluable subjects), mean, SD, and range for each treatment at each time point.

A mixed model repeated measure analysis of variance will be performed over mean sleep latency scores with treatment, period, time, and treatment*time as fixed effects; correlated observations coming from the same subjects will be adjusted using a subject level random effect and suitable covariance structure. The overall treatment effect for LML134 vs placebo will be reported along with a 95% CI.

11.5.2 Safety

All analysis will be performed under safety analysis set.

Vital signs

All vital signs data will be listed by treatment group, subject, and visit/time and if ranges are available abnormalities (and relevant orthostatic changes) will be flagged.

Summary statistics of height, weight, temperature, blood pressure, and pulse rate will be provided by treatment and visit/time using statistics like N, mean, median, standard deviation, and range.

The same data will be plotted using arithmetic mean-SD graphs over time for each parameter separately. Separate lines will be drawn for each treatment in order to see any potential differences.

ECG evaluations

All ECG data will be listed by treatment group, subject, and visit/time, and abnormalities will be flagged.

Each ECG parameter will be summarized by treatment, visit/time using statistics like N, mean, median, standard deviation, and range.

The same data will be plotted using arithmetic mean-SD graphs over time for each parameter separately. Separate lines will be drawn for each treatment in order to see any potential differences. Reference lines will be drawn for normal ranges (if available).

Clinical laboratory evaluations

All laboratory data (hematology, blood chemistry, urinalysis) will be listed by treatment, subject, and visit/time and if normal ranges are available abnormalities will be flagged.

Each laboratory parameter (hematology, blood chemistry, urinalysis) will be summarized by treatment, visit/time using statistics like N, mean, median, standard deviation, and range.

The same data (hematology, blood chemistry, urinalysis) will be plotted using arithmetic mean-SD graphs over time for each parameter separately. Separate lines will be drawn for each treatment in order to see any potential differences. Reference lines will be drawn for normal ranges (if available).

Adverse events

All information obtained on adverse events will be displayed by treatment group and subject.

The number and percentage of subjects with adverse events will be tabulated by body system and preferred term with a breakdown by treatment.

Furthermore, risk ratio of LML134 compared to placebo along with 95% confidence interval will be drawn in a forest-plot for each system organ class and preferred term.

An adverse event starting in one epoch and continuing into the next epoch is counted only in the onset period. A subject with multiple adverse events within a body system and treatment epoch is only counted once towards the total of this body system and treatment.

Other safety evaluations

All safety data will be listed by treatment, subject, and visit/time. Summary statistics for specific parameters will be reported based on clinical decision. Details of reporting will be mentioned in SAP.

Analysis of PSG data will be discussed in detail in SAP.

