8.6.4.3 Urinalysis

Dipstick measurements for protein, blood, and WBC/leukocytes will be performed. If the dipstick result is positive for protein, nitrite, leucocytes and/or blood, the sample will be sent for microscopic analysis of WBC, RBC and casts, furthermore the protein-creatinine ratio (PCR) and the albumin-creatinine ratio (ACR) will also be measured.

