7.2 Descriptive analyses

Subject demographics and other baseline characteristics

All data for background and demographic variables will be listed by treatment and subject. Summary statistics will be provided for all subjects, as well as for each treatment.

Relevant medical history, current medical conditions, results of laboratory screens, drug tests and any other relevant information will be listed by treatment and subject.

Treatment

Data for study drug administration and concomitant therapies will be listed by treatment and subject.

Vital signs

All vital signs data will be listed by treatment, subject, and visit/time and if ranges are available abnormalities (and relevant orthostatic changes) will be flagged. Summary statistics will be provided by treatment and time.

Summary statistics of height, weight, temperature, blood pressure, and pulse rate will be provided by treatment and time using statistics like N, mean, median, standard deviation, and range.

ECG evaluations

All ECG data will be listed by treatment, subject and time, abnormalities will be flagged. Summary statistics will be provided by treatment and time.

Each ECG parameter will be summarized by treatment, time using statistics like N, mean, median, standard deviation, and range.

The same data will be plotted using arithmetic mean-SD graphs over time for each parameter separately. Separate lines will be drawn for each treatment in order to see any potential differences. Reference lines will be drawn for normal ranges (if available).

Clinical laboratory evaluations

All laboratory data will be listed by treatment, subject, and time and if normal ranges are available abnormalities will be flagged. A separate listing is provided presenting all parameters in a subject with any abnormal values. Summary statistics will be provided by treatment and time.

Adverse events

All information obtained on adverse events will be displayed by treatment and subject.

The number and percentage of subjects with adverse events will be tabulated by body system and preferred term with a breakdown by treatment.

Separate tables will be presented indicating event severity and study drug relationship.

An adverse event starting in one period and continuing into the next period is counted only in the onset period. A subject with multiple adverse events within a body system and treatment period is only counted once towards the total of this body system and treatment.

Polysomnography

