7.3 Graphical presentation

Boxplots to visualize trends in longitudinal safety data (vitals, ECG, lab parameter, PSG) will be created.

ECG and vital signs data will also be plotted using arithmetic mean-SD graphs over time for each parameter separately. Separate lines will be drawn for each treatment in order to see any potential differences

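### Urinalysis is assigned means and SDs, but its routine result is a graded dipstick and its numeric results exist only after a positive one, so the plan needs counts over all tested subjects (minor, descriptive safety reporting)

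*Protocol*

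**What the plan says.** Protocol 11.5.2, under clinical laboratory evaluations, names urinalysis explicitly. For the tables: "Each laboratory parameter (hematology, blood chemistry, urinalysis) will be summarized by treatment, visit/time using statistics like N, mean, median, standard deviation, and range". For the graphs: "The same data (hematology, blood chemistry, urinalysis) will be plotted using arithmetic mean-SD graphs over time for each parameter separately". The graphs are meant for comparing treatments: "Separate lines will be drawn for each treatment in order to see any potential differences".

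Protocol 8.6.4.3 defines what is measured. Every scheduled sample gets a dipstick: "Dipstick measurements for protein, blood, and WBC/leukocytes will be performed". Further work is conditional: "If the dipstick result is positive for protein, nitrite, leucocytes and/or blood, the sample will be sent for microscopic analysis", and on the same trigger "the protein-creatinine ratio (PCR) and the albumin-creatinine ratio (ACR) will also be measured". Table 16-1 expresses dipstick proteinuria as a grade (1+ or more), which shows the scale is ordinal. Table 16-2 adds one other route to microscopy, the follow-up of a renal event.

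The SAP is less specific than the protocol. Section 7.2 names N, mean, median, SD and range for vital signs and ECG. For laboratory data it promises only summary statistics by treatment and time, plus listings with abnormalities flagged and this addition: "A separate listing is provided presenting all parameters in a subject with any abnormal values". Section 7.3 confines mean-SD graphs to ECG and vital signs, but includes laboratory parameters in the boxplots: "Boxplots to visualize trends in longitudinal safety data (vitals, ECG, lab parameter, PSG) will be created". Neither document plans a frequency or shift table for dipstick results, or a count of samples measured out of samples tested for PCR and ACR.

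**The concern.** Two kinds of result sit under the one word urinalysis, and neither suits the stated summary.

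- **Dipstick.** It is available for every scheduled sample but is graded. A mean and SD of grades have no useful interpretation.
- **PCR, ACR and microscopy.** They are numeric, but exist only where the dipstick was positive for any trigger marker. After dosing, that selection may itself be affected by treatment. Subjects with a clean dipstick contribute nothing, and the number contributing can differ between LML134 and placebo.

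Urinalysis is a named endpoint of the secondary objective on safety and tolerability compared with placebo (protocol 2.2, SAP 1.3.2). The quantity that answers it, how many subjects turned positive on each treatment, is not a planned summary. A treatment that produces extra mild positives adds low values to its own PCR mean, so that mean is a poor guide to the comparison.

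**Working it through.** No figure in the plan bears on this point, so there is none to reproduce. The documents give no dipstick-positive rate, PCR distribution or urinary drug effect. Every such value below is assumed.

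**1. How many numeric values would there be?** Inputs: 18 completers (SAP 1.4), 36 planned evaluable subjects (protocol 11.7), and an assumed positive rate p. Expected number = n × p. An SD needs two values, and P(fewer than 2) = (1−p)^n + n·p·(1−p)^(n−1).

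| p | Expected of 18 | P(<2), n=18 | Expected of 36 | P(<2), n=36 |
|---|---|---|---|---|
| 5% | 0.9 | 77% | 1.8 | 46% |
| 10% | 1.8 | 45% | 3.6 | 11% |
| 20% | 3.6 | 10% | 7.2 | 0.3% |
| 30% | 5.4 | 1% | 10.8 | <0.1% |

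**2. Can the subset mean mislead?** Take 18 subjects. On placebo, 2 are positive with PCR 200 mg/g each. On LML134, the same 2 are positive plus 4 new positives at 60 mg/g. Give clean samples an unmeasured PCR of 10 mg/g.

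- Subset mean: placebo 200 (n=2); LML134 (2×200 + 4×60)/6 = 107 (n=6). LML134 looks better.
- Count positive: 2/18 (11%) against 6/18 (33%). LML134 looks worse.
- Mean over all subjects, which the plan cannot compute: (400 + 16×10)/18 = 31 against (400 + 240 + 12×10)/18 = 42. LML134 is worse.

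**3. Is reversal the expected result?** Assume PCR on placebo is log-normal with median 60 mg/g and log-SD 0.7. The dipstick is positive for protein when PCR times a log-normal reading error (log-SD 0.4) exceeds 150 mg/g, the PCR level in Table 16-1. LML134 multiplies every PCR by r.

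Write S = √(0.7² + 0.4²) = 0.806 and m = ln(60r). Then
- P(positive) = Φ((m − ln 150)/S)
- E[PCR] = exp(m + 0.245)
- E[PCR | positive] = E[PCR] × Φ((m + 0.49 − ln 150)/S) / P(positive)

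For placebo (r=1): 12.8% positive, overall mean 77, mean among positives 179. For r=1.25: 19.5% positive, overall mean 96, mean among positives 197. The true ratio of 1.25 appears as 197/179 = 1.10. It is diluted but keeps its sign.

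Now let a fraction q of samples also be sent on for blood, leucocytes or nitrite, independently of PCR. The fraction sent is 1 − (1−P)(1−q), and the mean among those sent is [q·E[PCR] + (1−q)·P·E[PCR | positive]] / fraction sent. Placebo has q=0.10; LML134 still has r=1.25.

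- Placebo: 131 mg/g.
- LML134 with q=0.30 (20 extra points): 127 mg/g, slightly reversed.
- LML134 with q=0.50 (40 extra points): 112 mg/g, clearly reversed.

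**4. Chance of the wrong sign in one trial.** Simulation of 20,000 crossover trials under the step 3 model, with an additional assumed within-subject correlation of 0.5 on the log scale:

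| Pattern | Subset mean, n=18 / 36 | PCR measured in all, n=18 / 36 |
|---|---|---|
| r=1.25, protein trigger only | 38% / 35% | 13% / 5.5% |
| r=1.5, protein trigger only | 28% / 23% | 2% / 0.2% |
| r=1.25, 40 extra points on other markers | 63% / 70% | 12% / 5% |

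**5. When is the urine taken?** The assessment schedule has no urinalysis on Days 1 to 3. Completers' post-dose sample comes 7 to 14 days after treatment (protocol 3.1). With a half-life of 4.6 to 7.6 hours (protocol 3.3), 7 days is 168/7.6 = 22 to 168/4.6 = 37 half-lives.

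**The case against.** The other side has a good deal to say, and most of it limits the size of the point.

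- The SAP does not repeat the mean/SD list for laboratory data and plans no mean-SD graph for them. Its summary statistics could be read to include n (%). The protocol's own list is introduced loosely, as examples. This stands. But the SAP is where the discretion should be resolved, and it adds laboratory boxplots without a rule for urine.
- N would appear in a table following protocol 11.5.2, so an imbalance of 6 against 2 would be visible. This stands, though N without a denominator of subjects tested is not a rate.
- Renal alerts must be followed up (protocol 9.4), flagged listings are planned, and abnormalities that are clinically significant, symptomatic or need therapy become adverse events (protocol 9.1) tabulated by treatment. With 18 completers, positives can be counted from a listing. This stands. The gap is the missing treatment summary for positives below the adverse-event threshold.
- With a sample at least about 22 half-lives after dosing, no summary will say much about acute effects. This stands for completers.

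A reader might infer that the planned comparison will point the wrong way, or that it would hide a urinary signal. The documents do not support that. Reversal rests entirely on assumed values, a uniform PCR rise with protein as the only trigger gives dilution instead, and monitoring of individual subjects does not depend on these tables.

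**Conclusion.** The point holds as a minor defect in descriptive safety reporting. The method named in protocol 11.5.2 yields either means of grades or means in a subset selected on a post-treatment abnormality, and the SAP does not replace it with something suitable. That conclusion rests on the documents alone.

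The size rests on assumptions. At positive rates of 5% to 30%, 0.9 to 5.4 of 18 completers would have numeric values per treatment. A true PCR ratio of 1.25 shrinks to about 1.10 with a protein trigger only; reversal on average needs many extra positives on other markers. The primary endpoint, the proof-of-concept criteria and subject-level safety monitoring are unaffected. The statement that numeric values follow only a positive dipstick applies to scheduled samples; microscopy in renal-event follow-up is a further route, and also a selected one.

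**What to change.** In protocol 11.5.2 and SAP 7.2, give urinalysis its own rule. By treatment and visit, report:

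1. n (%) by dipstick grade for each marker;
2. n (%) newly positive relative to that period's own baseline;
3. n (%) meeting the PCR/ACR criteria of Table 16-1.

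The denominator for all three is treated subjects with a urinalysis at that visit. For item 3, state how the two-fold criterion is handled when no baseline PCR or ACR was measured, which will be usual. For item 2, state how a sample is used when the Period 1 follow-up visit also serves as Baseline 2.

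List PCR, ACR and microscopy values with the number measured out of the number tested. Take urinalysis out of the protocol's mean-SD tables and graphs and out of the SAP 7.3 boxplots. Also reconcile 8.6.4.3, which names nitrite as a trigger but not among the dipstick measurements.

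Cost: SAP wording, a matching protocol clarification and one table shell. No new data are needed, because urinalysis is already scheduled at both baselines and after each period. The downside is that numeric PCR and ACR means are no longer tabulated.
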